7.2.3 Number of Subjects Required

The total number of subjects to be enrolled in the study to meet sample size calculation requirements is 12, which includes 3 additional subjects to account for an expected dropout rate of 25%.

7.2.4 Vulnerable Populations

Pregnant and breastfeeding women have not been excluded from this low-risk study. The are no benefits associated for pregnant and breastfeeding women to participate but there also no risks identified if they were to participate. It is to be noted that whilst we are not excluding pregnant or breastfeeding women, we are also not targeting them either.

7.2.5 Recruitment and Study Duration

The following subject status definitions apply:

- Enrolled: A subject that has a signed the Informed Consent form for the study.
- Screen Fail: An Enrolled subject that has been determined to not meet one or more eligibility criteria.

- Participated: Subjects who have met eligibility criteria and have commenced baseline assessments.
- Withdrawn: An Enrolled subject who withdrew or was withdrawn by the Investigator or Sponsor before the expected End of Study visit. Withdrawn subjects may still continue in safety follow up until their scheduled End of Study visit, for reasons described in section 7.2.6.
- Completed: Enrolled subjects who complete the required treatment and visit schedule.

The recruitment period for the clinical investigation is estimated to be 4 weeks from the time of first subject consent to recruitment of the last subject.

The expected duration of each subject's participation in the clinical investigation, is up to 3 months, from the time of informed consent through to the last study visit.

Clinical Investigation completion is last subject last visit. In the event of an ongoing SAEs/SADEs at the time of this last visit, the clinical investigation completion will be extended for a further 30 days, or until resolution or stabilisation of the event, whichever comes first.

7.2.6 Criteria for Subject Withdrawal

Subjects can decide to withdraw from the investigation at any time. The Investigator shall ask the reason(s). The reason for withdrawal should be documented in the subject's source files and the case report form (CRF).

The Investigator or Sponsor may also decide to withdraw a subject from the clinical investigation if it is considered to be in the subject's best interests.

Subject withdrawal may be for any of the following reasons:

- Adverse Event (AE)
- Device Deficiency (DD)
- CIP or GCP deviation
- Subject withdrew consent
- Subject lost to follow-up
- Subject death
- Sponsor decision
- Investigator decision
- Other (specify)

If a subject is lost to follow-up, every possible effort must be made by the study site personnel to contact the subject and determine the reason for discontinuation. At least 3 separate attempts taken to contact the subject must be documented.

Participating subjects who are withdrawn/discontinued will not be replaced.

Clinical Investigation Plan: CLTD5818

7.2.7 Randomisation Procedures

No treatment randomisation is planned. However, to control for order effects during speech perception testing for the Primary and Secondary Endpoints a 4x4 balanced Latin square order will be implemented (see table 3).

	First Sound Processor	Second Sound Processor	Third Sound Processor	Fourth Sound Processor
SYD01, 05, 09	Kanso 2	Kanso 2 NF	Nucleus 8	Kanso 2 + FF
SYD02, 06, 10	Kanso 2 NF	Kanso 2 + FF	Kanso 2	Nucleus 8
SYD03, 07, 11	Kanso 2 + FF	Nucleus 8	Kanso 2 NF	Kanso 2
SYD04, 08, 12	Nucleus 8	Kanso 2	Kanso 2 + FF	Kanso 2 NF

Table 3. Order of Administration of the Speech Perception Tests

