7.1.1 Design Rationale

Experienced adult cochlear implant recipients have been chosen as the study population due to their ability to compare Sound Processors across generations, in and outside of the booth. In addition, performance benefits achieved by adults can generally be extrapolated to younger age groups, avoiding the need to recruit this vulnerable population.

Comparison will be made within subjects with repeated measures for each of the sound processing conditions to be evaluated. There will be two test sessions with no take home use between sessions. The test sessions will include words in quiet tests. These speech measures are routine outcome measures used to evaluate new signal processing algorithms and hardware.

There will be no blinding of the study investigators.

Blinding of the study subject will be undertaken where possible, particularly when multiple signal processing conditions are loaded onto a single study device. Patients will not be told which program will be used in which order, and because the Kanso 2, Kanso 2 NF and Kanso 2 FF Sound Processors are physically identical, it may also be possible to conceal which Sound Processor is being used during testing.

Counterbalancing of the test order will be undertaken where possible to limit the influence of order effects on results.

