7.6 Sponsor Role in Conduct of the Clinical Investigation

Sponsor and investigator roles are assumed by Cochlear employees.

Cochlear has designed and will execute this clinical trial in-house at Cochlear Limited, Sydney. The study site consists of a small team of Investigators, trained as clinical Audiologists, to execute this research activity. Investigators are qualified audiologists familiar with cochlear implant development, surgery and programming. Investigators' trial materials and testing rooms (sound booths) are securely separated from Sponsor facilities. The trial investigators, or delegates within the study site, will enter the data into the eCRF.

The study is planned, designed and developed by a separate group within Cochlear, known as Clinical Affairs (the Sponsor). Cochlear has SOPs to manage the separation of Investigator and Sponsor activities as well as ensure they align with all applicable regulations.

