8.3 Risks Associated with Participation in the Clinical Investigation

There is a small risk that programs on the Kanso 2, Kanso 2 NF and Nucleus 8 Sound Processors may sound different to each user's own Sound Processor; this is unlikely if study subjects enter the study already using a Nucleus 7 or Kanso 2 Sound Processor and more likely if they enter a study with a legacy device. If subjects experience sound that is uncomfortable, they are counselled to remove the Sound Processor off their head or ask the research audiologist to immediately cease stimulation. Other risks may include exacerbation of existing tinnitus and a reduction in the sound quality or intelligibility of the research programs. Subjects are advised to return to their own processor and promptly inform the investigators if these events occur.

Warnings and contraindications

See the Nucleus 7 and Kanso 2 Sound Processors User Guide for all Warnings and Contraindications. (user guides can be found within the 'Support' section of the country specific Cochlear website; www.cochlear.com). At this preliminary stage in development, the Nucleus 7 Sound Processor User Guide will be relevant for Nucleus 8 Sound Processor.

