9.4 Sample Size Determination

This study is a non-inferiority design, and sample size calculation was based on non-inferiority tests for CNC word scores. The sample size using a confidence interval method (two-tailed 95% confidence interval) was estimated to have a reasonable power to detect non-inferiority word scores for the listed hypotheses.

To reject the null hypothesis of inferior word perception in quiet for the New processor:

- A margin of non-inferiority of 10% (new-old) has been chosen. That is saying that a true mean difference of anything up to 10% is acceptable and not clinically meaningful. This margin is based on clinical consensus, and previous feedback from the FDA
- An expected standard deviation of difference scores of 7.5% for CNC words (50 dB), based on previous OTE studies investigating words in quiet.
- A significance level $\alpha = 0.05$ (two-tailed).
- A desired power of 0.9.

Based on these assumptions, a sample size of 9 subjects is required to reject the null hypothesis. An increased sample size of 12 subjects will be enrolled, which will allow for the possibility that the variability in difference scores will be greater than expected and to account for the possibility of subject attrition.

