9.6 Primary Endpoint Analyses

Primary and Secondary Speech Perception Endpoints:

Words in quiet scores at different speech testing conditions will be listed and summarised descriptively by treatment group and study population. Figures as appropriate to further describe the data may be presented.

For the non-inferiority test of words in quiet scores, the 95% CI (alpha=0.025 one-sided) for the mean paired difference will be estimated. If the lower limit of the 95% CI of the mean paired difference is above -10%, the treatment condition is regarded as non-inferior to the control in term of words in quiet perception. The non-inferiority margin of -10% for words in quiet scores (monosyllables) is also based on clinical consensus.

If non-inferiority is demonstrated, the testing will proceed to a test of superiority.

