## 1.4 Randomisation, Matching and Blinding

No treatment randomisation is planned. However, to control for order effects during speech perception testing for the Primary and Secondary Endpoints a 4x4 balanced Latin square order will be implemented (see table 3).

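### Test order is tied to subject number, neither randomised nor concealed; this biases the paired contrasts only if within-session trend differs by subject type and type is linked to order

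*Protocol*

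**What the plan says.** Protocol 7.2.7 states "No treatment randomisation is planned. However, to control for order effects during speech perception testing for the Primary and Secondary Endpoints a 4x4 balanced" design, a Latin square, will set the order of testing. SAP 1.4 repeats "No treatment randomisation is planned". Table 3, identical in both documents, prints the subject numbers beside each order in a repeating cycle of four: SYD01, 05 and 09 take row 1, SYD02, 06 and 10 take row 2, and so on to SYD12.

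On who knows the order, protocol 7.1.1 says "There will be no blinding of the study investigators", and 7.6 says "Sponsor and investigator roles are assumed by Cochlear employees". Section 7.2.7.1 withholds the order from the subject only. Neither document describes concealment from the site, or says how or when subject numbers are issued.

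On order effects, protocol 9.5 says period and sequence effects will not be assessed and will not bias the conclusion. SAP 8.1 adds a supportive ANOVA with device, period, sequence and subject-within-sequence terms. SAP 5.6 counts a wrong test order as a major deviation.

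**The concern.** Investigators judge several eligibility items themselves (fluency, implant location, ability to comply) and know each candidate's own processor, which is inclusion criterion 5. If numbers run consecutively, they also know the order attached to the next number before deciding whom to book. Nothing in the design then prevents a type of subject from becoming associated with a type of order.

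The association would matter because of how Table 3 is laid out. In rows 1 and 4, both Kanso 2 NF and Kanso 2 + FF are tested after the Kanso 2 control; in rows 2 and 3 both are tested before it. If subjects who improve during the session sat mainly in rows 1 and 4, both contrasts would move toward non-inferiority. The square protects against a trend shared by all subjects. It does not protect against a trend that differs between subjects when that difference is tied to the row.

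**Working it through.** **Plan's own figure.** Inputs from protocol 9.4 and 9.6: "A margin of non-inferiority of 10% (new-old) has been chosen"; SD of paired differences 7.5; "A desired power of 0.9"; and "the 95% CI (alpha=0.025 one-sided) for the mean paired difference will be estimated". Assuming a true difference of 0, which the documents do not state, the paired non-inferiority t-test (noncentral t) has power 0.896 at n = 8 and 0.937 at n = 9. The stated 9 reproduces, and 9/(1 − 0.25) = 12 enrolled. Randomising the order leaves both unchanged.

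**Balance of Table 3.** Each condition appears once in each position, and each of the 12 ordered neighbouring pairs appears once. Lags (position of treatment minus position of control):

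| Contrast | Row 1 | Row 2 | Row 3 | Row 4 | Sum |
|---|---|---|---|---|---|
| NF − Kanso 2 | +1 | −2 | −1 | +2 | 0 |
| FF − Kanso 2 | +3 | −1 | −3 | +1 | 0 |

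With three subjects per row, a trend common to all subjects contributes trend × 3 × 0 / 12 = 0.

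**Does linking type to order bias the contrast by itself?** In simulation with type fully linked to row (one type in rows 1 and 4, the other in rows 2 and 3), a 20-point ability gap between types gave mean error −0.003 (NF) and 0.009 (FF). Adding a common trend of 2 points per position still gave about −0.02 for both. So it does not.

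**When bias appears.** Suppose 6 of 12 subjects gain b points per position and 6 gain none. Bias = b × (sum of the gainers' lags) / 12.

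- All six in rows 1 and 4 (worst case): NF 3 × (1 + 2)b/12 = 0.75b; FF 3 × (3 + 1)b/12 = 1.0b.
- First six, SYD01–06 (rows 1, 2, 3, 4, 1, 2): NF (1 − 2)b/12 = −0.08b; FF (3 − 1)b/12 = +0.17b.
- Last six, SYD07–12 (rows 3, 4, 1, 2, 3, 4): NF +0.08b; FF −0.17b.
- Least favourable run of six, such as SYD04–09 (rows 4, 1, 2, 3, 4, 1): NF (2 + 1)b/12 = 0.25b; FF (1 + 3)b/12 = 0.33b.

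**Effect on the decision.** Chance of declaring non-inferiority at a true difference of −10, with n = 12 and SD 7.5, by simulation (nominal 2.5%). The b values are assumptions.

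| All gainers in rows 1 and 4 | b = 1 | b = 2 | b = 3 |
|---|---|---|---|
| NF bias (points) | 0.75 | 1.5 | 2.25 |
| NF false non-inferiority | about 5% | about 8.5% | about 13% |
| FF bias (points) | 1.0 | 2.0 | 3.0 |
| FF false non-inferiority | about 6% | about 11% | about 18% |

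A pure-shift calculation that holds the SD at 7.5 gives somewhat higher rates: 5.0%, 9.3% and 15.6% for NF, and 6.2%, 13.3% and 24.4% for FF. In the simulation the unequal lags also widen the observed SD. With the first or last six as gainers and b from 1 to 3, the rate is 0.6% to 2.7%. With the same gainers randomly assigned to rows, expected bias is 0 and the rate is 1.8% to 2.5%.

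**Supportive ANOVA.** Fitted to noise-free data with b = 2 and gainers in rows 1 and 4, the SAP 8.1 model returned NF − Kanso 2 = −8.5 for a true −10, and FF − Kanso 2 = +2.0 for a true 0. These are the worst-case biases of 1.5 and 2.0. The model is additive, so in the complete balanced square its device difference equals the simple paired mean.

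**The case against.** The tempting stronger reading is that a predictable order in itself biases the NF and FF results, or that the site could steer the outcome. The documents do not support either.

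- Every subject receives all four conditions, so there is no arm to steer anyone into, and the checks above show that linking type to row is harmless on its own.
- Haphazard booking is unlikely to produce the worst case. Rows 1 and 4 are SYD01, 04, 05, 08, 09 and 12, and a cycle of four spreads neighbouring bookings over all rows. If arrival is unrelated to type, all six gainers fall in those rows with probability 1/924, and five or more with probability 37/924 = 4.0%.
- Within-session gain is not observed before consent. The only proxy is the subject's own processor. Protocol 8.3 calls it a small risk that test programs sound different and adds "this is unlikely if study subjects enter the study already using a Nucleus 7 or Kanso 2 Sound Processor and more likely if they enter" with a legacy device. That is a risk statement and gives no rate of adaptation.
- Values of b = 2 or 3 mean 6 or 9 points gained between positions 1 and 4 in half the subjects and none in the rest, against a margin of 10. Both documents expect period and sequence effects to be minimal.
- Consecutive numbering is not stated. Enrolment is defined by signed consent (7.2.5), so screen failures could use up numbers.
- The ANOVA's period term would reveal an average trend (b/2 per position here), although not that it differs by type.

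All of this stands, and it lowers the severity. It does not supply random assignment or concealment, and it leaves the planned analyses unable to remove the bias if it occurred. The assurance in protocol 9.5 therefore rests on expectation where the design could have guaranteed it.

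**Conclusion.** This is a low-severity design weakness. Order is fixed by subject number and open to unblinded, sponsor-employed investigators. Two conditions must both hold before the NF or FF contrast is biased: the within-session trend differs between types of subject, and type is selectively linked to rows 1 and 4. The ceiling is then 0.75b for NF and 1.0b for FF; clustered booking gives at most about 0.25b and 0.33b. These figures assume 12 completers, three per row, an even split of types and a linear trend. The value of b is an assumption throughout, so the error rates are a worst-case range and not a forecast. A reader should not infer that the results are biased or that steering is expected.

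**What to change.** Keep the four orders in Table 3 and three subjects per order. Before the first consent, have the statistician generate a random list of orders balanced over the four rows. Hold it outside the site, for example behind the role-based permissions of the data capture system described in protocol section 14. Release each subject's order only after eligibility is confirmed. Remove the SYD numbers from Table 3, and amend protocol 7.2.7 and SAP 1.4 to say that subjects are randomly assigned to one of the four test orders, concealed from the investigator until eligibility is confirmed.

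Whether to use blocks of four or one permutation of 12 slots is the statistician's choice. A single permutation is harder to guess. Blocks keep the rows more even after dropout, which matters because withdrawals are not replaced: with 9 completers and badly uneven rows, a common trend of 1 point per position can leave up to 0.67 points (NF; rows 3, 0, 3, 3) or 1.0 point (FF; rows 3, 3, 0, 3).

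The cost is a short wording change, one list and one release step per subject. There are no extra subjects, visits or tests, and the primary analysis is unchanged. The fix does not address unblinded testing and scoring, which is a more direct route to bias and needs its own answer.

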7.2.7.1 Blinding Procedures

For in booth speech perception testing, the test order will not be revealed to the study subject. The counterbalancing as outlined in section 7.2.7 will be used to ensure that there is a balanced order or test conditions.

7.2.8 Post-investigation Medical Care

At the end of the study, subjects will return all investigational devices to the investigator and return to their own hearing devices. Subjects will continue to be clinically managed by their regular clinician according to their clinic's standard practice after the clinical investigation has been completed.

7.3 Performance Evaluations and Procedures

Speech perception in quiet

Speech perception in quiet will be measured using the CNC monosyllabic words at 50 dB from S0 (zero degrees azimuth) position. There will be 2 lists per treatment or control (see Table 4 for Input processing conditions). The goal of speech perception assessment in quiet is to compare percent words and phonemes correct for each of the sound processing combinations.

Participant Evaluations and Procedures

Screening Visit

Included in this period:

- Written informed consent
- Eligibility including sentence in babble test if required
- Case Report Form Completion

Informed consent

See Section 10

Screening

Study investigators will screen each patient according to the inclusion and exclusion criteria. For subjects without relevant speech perception data on file, a words in quiet test will be conducted at 50 dB SPL. A score of 30% or more in the CI alone condition is required to pass that specific inclusion criteria. Subjects will be tested with their own sound processor and their own preferred signal processing settings for quiet environments.

All subjects will be tested in the unilateral condition and each subject will have their contralateral ear (non-test ear) blocked with an ear plug. Subjects with bilateral implants that meet the inclusion criteria will be tested using the subject's preferred ear or if the preferred ear is not known then the first implanted ear will be used as the test-ear.

The subject will be positioned so that the middle-point between the two ears is centred at the reference point of the sound field. The loudspeaker should be positioned at the same height as the middle-point of the two ears.

The AuSTIN software will be used to present the test material. The investigator, or suitably qualified delegate will use the software to select:

- CNC word test
- 50 dB SPL presentation level
- Signal from in front (0 degrees)
- 1 list of 50 words

At the end of each run, the investigator will record the result on the worksheet and in the EDC.

Subjects must be consented and enrolled to the study and inclusion and exclusion criteria confirmed prior to any study activities starting.

Case Report Form

Once enrolled, the investigators will complete the following CRFs for each study subject.

- Demographics
- Medical history
- Hearing history
- Device history

Visit 1

Included in this period:

- Device Fitting
- Speech perception in quiet testing
- Case Report Form Completion

Device Fitting

Prior to assessing speech perception in quiet, the test Sound Processors will be loaded according to the input processing settings identified in Table 4.

ADRO is the adaptive dynamic range optimisation processing setting, and ASC is the auto sensitivity processing setting, both of which will be enabled or disabled in the test Sound Processors according to each subject's preferred settings on their own MAP; if the study subject uses and prefers ADRO and ASC in their own Sound Processor, then these setting will be enabled in the study Sound Processor.

SNR-NR is a single channel noise reduction algorithm and directionality refers to the microphone directionality that will be enabled. These signal processing settings will be enabled/disabled via the fitting software CDI Tool and Custom Sound Pro.

Speech perception in quiet test

In booth speech perception testing will be conducted using the input processing combinations and hardware listed in Table 4. The order of testing will be conducted according to the counterbalancing outlined in Section **Error! Reference source not found.**

	Notch filters	WNR	SNR-NR	Directionality	ADRO & ASC	FF
Kanso 2		~	~	Std	As per user preference	
Kanso 2 NF	×	✓	~	Std	As per user preference	
Nucleus 8		~	~	Std	As per user preference	
Kanso 2 FF		×	~	Std	As per user preference	✓(Mild)

Table 4. Speech in Quiet test conditions.

Wind Noise Reduction (WNR); Signal to Noise Ratio- Noise Reduction (SNR-NR); adaptive dynamic range optimisa ion (ADRO); auto sensi ivity (ASC); ForwardFocus (FF)

All subjects will be tested in the unilateral condition and each subject will have their contralateral ear (non-test ear) blocked with an ear plug for all test conditions. Subjects with bilateral implants that meet the inclusion criteria will be tested using the subject's preferred ear or if the preferred ear is not known then the first implanted ear will be used as the test-ear.

The subject will be positioned so that the middle-point between the two ears is centred at the reference point of the sound field. The loudspeaker should be positioned at the same height as the middle-point of the two ears.

The AuSTIN software will be used to present the test material. The investigator, or suitably qualified delegate will use the software to select:

- CNC word test
- 50 dB SPL presentation level
- Signal from in front (0 degrees)
- 2 lists of 50 words each

At the end of each run, the investigator will record the result on the worksheet and in the EDC.

Case Report Form

- Concomitant medications/therapies
- Adverse events
- Device deficiencies
- Device exposure

End of visit and return of study devices

Included in this period:

- End of study and return devices

After the speech perception evaluation has been completed, study subjects will return the study devices and will use their own device as normal in their home environment in between speech evaluation study visits.

Adaptive procedure:

Although no product changes are expected during the study period, early product can be sensitive to the low-risk issues identified in

Table 1. During this feasibility study these product issues may be identified by study subjects during the acute testing sessions that require optimisation or correction, and an adaptive procedure allows for product feedback to be collected from study subjects, for the product to be updated, and for the updated product to be reissued to study subjects for continued testing. Table 5 identifies how issues will be investigated and retested by the research subjects.

New Device Iteration:

If a product issue is identified either prior to or during the speech perception evaluation that may have an impact on speech perception outcomes, the study will be paused for all subjects while the change is made and a new version of the Sound Processor system will be developed and issued to study participants.

If the product issue was present for all subjects, then all subjects will be asked to repeat any testing that had occurred

Category	Example of a product issue	Action
Sound quality	Study subjects may provide feedback on the general sound quality of the Sound Processor in everyday sound environments like noisy cafes, quiet rooms or windy situations.	If the issue has an impact on performance the product will be updated and speech perception will be re-evaluated by subjects.
	Study subjects may provide feedback that the Sound Processor is unacceptably noisy or has an unacceptably noticeable buzzing.	If the issue has an impact on performance the product will be updated and speech perception will be re-evaluated by subjects.
Intermittency	Study subjects may provide feedback that the Sound Processor is not outputting a consistent signal with gaps in stimulation.	If the issue has an impact on performance the product will be updated and speech perception will be re-evaluated by subjects.
General bugs and product issues:	While all measures have been undertaken to test each of the features with the investigational sound processor, there may be unforeseen issues that are exposed through usage in the environments used in the study.	General issues will be judged on a case by case basis. If it is judged that the issue has an unacceptable impact on performance, the product will be updated and re-evaluated by subjects.

Table 1. Product adaptation categories and product issue ex	examples
---	----------

All product issues will be recorded as device deficiencies. The Sound Processor will be considered mature for speech perception testing when all product optimisations that impact on performance have been made.

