2 CLINICAL INVESTIGATION SYNOPSIS

Investigation title	A Pre-Marketing, Prospective, Single-Site, Op en-Label, Wi t hin-Subject, Pilot, Interventional Study of Adult Cochlear Implant Speech Perception with the Kanso 2 (CP1150) So und Processor Compared with the Next Generation of Signal Processing Technology
Short title	OPTIMUM Study
Investigation number	CLTD5818
Name of	Kanso 2 Notch Filter (NF) Sound Processor
investigational medical device(s)	Kanso 2 Sound Processor with Forward Focus (FF)
	 CDI Tool Version 7.3.1(used in conjunction with Kanso 2 Sound Processors for programming NF and FF to device)
	Nucleus 8 (CP1110) Sound Processor (Unapproved device)
Intended use of investigational medical device(s)	The intended use and indications for use for the Kanso 2 NF Sound Processor is the same as the Kanso 2 (CP1150) Sound Processor. Intended Use: The Kanso 2 NF Sound Processor is intended to restore a level of meaningful hearing by capturing environmental acoustic sounds and/or sound from auxiliary wireless devices; processing the audio and communicating the processed audio to a compatible implant to provide electrical stimulation to the cochlea, or electrical stimulation of the auditory brainstem. While the Kanso 2 NF Sound Processor is intended to be compatible and
	can be used with Hybrid implants it is not intended to provide acoustic stimulation.
	Medical Indications for Use: The Kanso 2 NF Sound Processor requires a compatible Cochlear implant, see listed below:
	Freedom Hybrid: CI24RE (H), CI24RE (S)
	• Freedom Series Implants: CI24RE (ST), CI24RE (CA), CI24RE (CS), CI422
	• CI600 Series Implants : CI612, CI613, CI622, CI624
	CI500 Series Implants : CI512, CI513, CI522, CI532, CI551 Double Array and ABI541
	• N24 Series Implants: CI24R (CS), CI24R (CA), CI24R (ST), CI24M, CI11+11+2M, CI24MH (also known as CI6+16+2M) and ABI24M
Name and description	Kanso 2 (CP1150) Sound Processor
of comparator device/product(s)	Custom Sound Pro 6.3
	The Nucleus 8 and Kanso 2 Processing Units are intended to be used in combination with other devices as part of a hearing implant system to provide hearing sensation. The processing unit converts sounds into electrical signals, which it sends, via a coil, to an implant. The processing unit also provides power to the implant.
	When used in combination with an audio receiver, the Sound Processor also delivers sound to the ear canal in recipients with residual hearing.

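### Does the device-update and re-test procedure in CIP 7.3 need a score-blind trigger and a rule for which scores are analysed?

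*Protocol*

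**What the plan says.** The adaptive procedure in CIP 7.3 states that no product changes are expected. It still provides for them. A pause and a new device version follow "If a product issue is identified either prior to or during the speech perception evaluation that may have an impact on speech perception outcomes". The product-issue table in the same section gives sound quality, noise or buzzing, and intermittency as examples, each framed as feedback from subjects, with the action "If the issue has an impact on performance the product will be updated and speech perception will be re-evaluated by subjects". A last row covers general bugs, judged case by case: "If it is judged that the issue has an unacceptable impact on performance, the product will be updated and re-evaluated by subjects".

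On who repeats, the CIP says: "If the product issue was present for all subjects, then all subjects will be asked to repeat any testing that had occurred". On when the device is ready, it says: "The Sound Processor will be considered mature for speech perception testing when all product optimisations that impact on performance have been made". All product issues are recorded as device deficiencies.

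On blinding, CIP 7.1.1 says "There will be no blinding of the study investigators", and CIP 7.3 adds "At the end of each run, the investigator will record the result on the worksheet and in the EDC". Test order is hidden from subjects (CIP 7.2.7.1).

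The analysis sections do not mention repeats. SAP 5.1 and 5.2 set a minimum of one paired measurement for entry to the ITT and PP sets. SAP 6.1 has all data listed, SAP 6.2 rules out imputation, and the supportive ANOVA in SAP 8.1 has terms for device, period, sequence and subject only.

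**The concern.** The person who may judge that an issue affects performance can see the scores, and the CNC score is the study's only performance measure. If low scores prompted an update that changed nothing, the repeat would tend to be higher through regression to the mean. That favours non-inferiority for the notch filter (primary) and for ForwardFocus. For the Nucleus 8 comparison the direction reverses. Nucleus 8 is the control in SAP 3.1.3 but is also listed as investigational ("Nucleus 8 (CP1110) Sound Processor (Unapproved device"), so updating it after low scores works against Kanso 2.

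Separately, first, final or mixed-version scores would all satisfy the wording of the analysis sets, and the CIP states who repeats only when the issue was common to all. An analyst who kept scores from a faulty version could lose a true non-inferiority result.

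**Working it through.** **1. The plan's own figure.** Inputs from CIP 9.4: margin 10, SD of differences 7.5, one-sided alpha 0.025, power 0.9. The true difference is taken as 0 (assumed). For a paired t-test, power = P(T > t(0.975, n-1)), where T is noncentral t with noncentrality 10√n/7.5.

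- n = 8: noncentrality 3.77, power 89.6%
- n = 9: noncentrality 4.00, power 93.7%
- n = 12: noncentrality 4.62, power 98.7%

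Nine is the smallest n that reaches 90%, and 9/(1 - 0.25) = 12. Both planned numbers reproduce.

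**2. What starts a repeat.** Every specific example in the CIP 7.3 table is a subject's report of how the device sounds or behaves. A judgement about performance follows that report. The general-bugs row is wider, but it still begins with a product issue. A low CNC score is nowhere named as a trigger.

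**3. If scores did drive the decision.** Assumptions: true difference -10, an update with no real effect, 50-80% words correct, latest score analysed. Each condition has 2 × 50 = 100 words, so the test-noise SD of a difference is 100√(2p(1-p)/100): 7.07, 6.75 and 5.66 for p = 0.50, 0.65 and 0.80. The remaining between-subject SD is √(7.5² - noise²): 2.50, 3.28 and 4.92. Simulated one-sided error, n = 9 and 12:

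| Rule for repeating | Error |
|---|---|
| No repeat, or a pause unrelated to scores | 2.5% |
| Pause half-way because the running mean is below -10 | 3.1-3.6% |
| Pause at the first difference 1.5 SD low; all tested so far repeat | 3.0-3.7% |
| Same trigger; only that subject repeats | 3.1-4.2% |
| Full repeat after a complete failing run | 4.6-4.9% |
| First two pause rules mirrored, Nucleus 8 (control) updated | 1.4-2.3% |

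The bias of the mean under the two pause rules and the single-subject repeat is 0.3-0.7 points. The result depends on the assumed rule. Re-testing every subject below a cut-off between -25 and -10, with the test-noise share of the variance set at 50-100%, gives 2.5-12% if only the treatment device is repeated, and up to 32% if both devices are.

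**4. How often such triggers would fire.** At the margin, the half-way rule fires in 50% of trials and the 1.5 SD rule in 46-56%. With a true difference of 0 and n = 12, the same absolute cut-offs fire rarely:

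- mean of six below -10: Φ(-10/(7.5/√6)) = 0.05%
- any of twelve below -10 - 1.5 × 7.5 = -21.25: 1 - (1 - Φ(-21.25/7.5))^12 = 2.7%

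**5. If faulty-version scores were kept.** True difference 0 for the final device, and a 10-point fault in 1, 2 or 3 subjects whose old scores stay in: power falls from 98.7% to 95.6, 89.8 and 80.0% (n = 12), and from 93.7% to 82.6, 66.9 and 49.2% (n = 9). These losses require the analyst to retain scores that CIP 7.3 says are to be re-evaluated.

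**6. Whether a tighter rule would gain anything.** Suppose only final-version pairs are analysed, and re-testing subjects whom the fault did not touch is left optional. Unblinded staff could then choose who enters the primary set. With n = 12, a score-blind pause after six, no device effect and a true difference of -10, re-testing only the two or three highest of the first six gives an error of about 2.9-4.5% and a bias of +0.2 to +0.8 points. That is as large as the moderate cases in step 3. Re-testing Kanso 2 for one comparison only would also leave two Kanso 2 scores per subject, with no rule for the SAP 8.1 ANOVA.

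**The case for a change.** The best case for a change is that it is cheap and that the gap does not depend on suspicion. Once an iteration has happened, choosing the data set with scores in hand is less credible than choosing it beforehand. The threshold is also worded in more than one way, and no decision-maker is named.

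Part of this stands. The analysed version is not named in CIP section 9 or the SAP. The scope of repeats is not stated when only some subjects had the issue, though that CIP sentence ends without punctuation just before a table, so text may have been lost in extraction. Nothing makes the decision score-blind.

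The rest is weaker. The at-least-one-pair wording in SAP 5.1 and 5.2 is an entry rule for a study with several comparisons, not permission to choose among repeats. The unacceptable-impact wording belongs to the general-bugs row only. Other controls leave a trail: software versions are tracked (CIP 12), product issues are logged as deficiencies (CIP 7.3) and assessed by the Clinical Review Board (CIP 11.4.2), changes to investigation procedures need a documented amendment (CIP 18), major deviations are settled before database lock (SAP 5.2), and all collected data are listed (SAP 6.1). A selective repeat would therefore be visible in the report.

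**Conclusion.** No change to the plan is needed. The missing detail is one that analysts would fill sensibly. CIP 7.3 has testing repeated on the updated product and treats the device as ready only after optimisation, so the re-evaluated scores of the final device are the evident data set. With a fault common to all subjects, everyone repeats and the comparison remains sound.

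The bias needs four things together: an iteration, a decision influenced by scores, an update with no effect, and a true difference at the margin. Under moderate assumed triggers that gives about 3.0-4.2% against 2.5%, and 0.3-0.7 points against a 10-point margin. Larger figures need aggressive subject-level re-testing that the documents do not describe. No figure in the documents fixes the trigger rule, so all of these sizes are illustrations.

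Whether to keep scores from those who judge device faults is a fair trade-off. It would protect the error rate slightly, but a fault visible only in the scores could not prompt a repair, in a pilot whose stated purpose is to inform design.
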